3 LIST OF ABBREVIATIONS

ABT	Add-Back Therapy
AE	Adverse Event
ALT	ALanine amino Transferase
APTT	Activated Partial Thromboplastin Time
AST	ASpartate amino Transferase
AUC	Area Under the Curve
B-ALP	Bone-specific Alkaline Phosphatase
BMD	Bone Mineral Density
BMI	Body Mass Index
BP	Blood Pressure
bpm	Beats Per minute
°C	Degree Celsius
CK	Creatine Kinase
ClinRO	Clinician Reported Outcome
COC	Combined Oral Contraceptive
CRA	Clinical Research Associate
CRO	Contract Research Organization
C-SSRS	Columbia-Suicide Severity Rating Scale
CTx	C-terminal telopeptide
CV	Coefficient of Variation
CYP	Cytochrome P
DMC	Data Monitoring Committee
dPGIS	Patient Global Impression of Severity – daily recall
DXA	Dual-energy X-ray Absorptiometry
DYS	Dysmenorrhea
E2	Estradiol

EAP	Endometriosis-Associated Pain
ECG	ElectroCardioGram
eCRF	Electronic Case Report Form
eDiary	Electronic Diary
EHP-30	Endometriosis Health Profile – 30
ePRO	Electronic Patient Reported Outcome
EQ-5D-5L	EuroQol 5 Dimension 5 Level questionnaire
EU	European Union
ExFU	Extension Follow-Up
FD	Fixed Dose
FDA	Food and Drug Administration
FSH	Follicle-Stimulating Hormone
GCP	Good Clinical Practice
γ GT	Gamma-Glutamyl Transferase
GMP	Good Manufacturing Practice
HDL	High Density Lipoprotein
HIV	Human Immunodeficiency Virus
HRPQ	Health-Related Productivity Questionnaire
HRUQ	Health Resource Utilization Questionnaire
IB	Investigator Brochure
ICF	Informed Consent Form
ICH	International Conference on Harmonization
IEC	Independent Ethics Committee
IMP	Investigational Medicinal Product
INN	International Nonproprietary Name
INR	International Normalized Ratio
IRB	Institutional Review Board

IUD	Intra-Uterine Device
IWRS	Interactive Web Response System
LDH	Lactate DeHydrogenase
LDL	Low Density Lipoprotein
LFT	Liver Function Test
LH	Luteinizing Hormone
LOQ	Limit Of Quantification
MCH	Mean Corpuscular Haemoglobin
MCHC	Mean Corpuscular Haemoglobin Concentration
MCV	Mean Corpuscular Volume
mg	Milligram
min	Minute
MME	Morphine Milligram Equivalent
mPGIS	Patient Global Impression of Severity – monthly recall
mmHg	millimeter of mercury
msec	Millisecond
NETA	NorEThisterone Acetate
NMPP	Non-Menstrual Pelvic Pain
NRS	Numeric Rating Scale
NSAID	Non Steroidal Anti-Inflammatory Drug
OAT3	Organic Anion Transporter 3
OBE2109	(2-Hydroxyethyl)trimethylammonium-3-[2-fluoro-5-(2,3-difluoro-6-methoxybenzyloxy)-4-methoxyphenyl]-2,4-dioxo-1,2,3,4-tetrahydrothieno[3,4-d]pyrimidine-5-carboxylate
P1NP	Procollagen type 1 N-terminal Propeptide
P4	Progesterone
PAP	PAPanikolaou test
PD	PharmacoDynamic

PGIC	Patient Global Impression of Change
PPGIC	Post-treatment Patient Global Impression of Change
PGIS	Patient Global Impression of Severity
PK	PharmacoKinetic
PSF	Pregnancy Surveillance Form
PSIQ	Physician Surgery Intention Question
PVC/Al	PolyVinyl Chloride/Aluminum
QC	Quality Control
QD	Once daily (from the Latin Quaque Die)
QoL	Quality of Life
QTc	QT interval corrected for heart rate
QTcF	QT interval corrected for heart rate (QTc) using Fridericia's correction formula
RBC	Red Blood Cell
SAE	Serious Adverse Event
SAP	Statistical Analysis Plan
SERM	Selective Estrogen Receptor Modulator
SHBG	Sex Hormone-Binding Globulin
SIN	Subject Identification Number
SPRM	Selective Progesterone Receptor Modulator
SSIQ	Subject Surgery Intention Question
SUSAR	Suspected Unexpected Serious Adverse Reaction
TD	Titrated Dose
TEAE(s)	Treatment Emergent Adverse Event(s)
TVUS	TransVaginal UltraSound
ULN	Upper Limit of Normal
US/USA	United States/United States of America

VAS	Visual Analogue Scale
VRS	Verbal Rating Scale
WBC	White Blood Cell

4 SYNOPSIS

Study Title: A double-blind randomized extension study to assess the long-term efficacy and safety of linzagolix in subjects with endometriosis-associated pain

Code/Name ObsEva Investigational Drug: linzagolix (OBE2109) **Phase of Development:** 3

Objectives:

The primary objective of this extension study is to assess the maintenance of efficacy of linzagolix administered orally once daily for up to an additional 6 months (for up to 12 months of treatment in total) in women who have already completed 6 months of linzagolix treatment at a dose of 75 mg alone or of 200 mg in combination with add-back therapy (estradiol (E2) 1 mg / norethisterone acetate (NETA) 0.5 mg) in the management of moderate to severe endometriosis-associated pain (EAP) in women with surgically confirmed endometriosis. The two co-primary efficacy endpoints will be clinically meaningful reduction over the last 28 days of randomized treatment up to the Month 12 visit, along with a stable or decreased use of analgesics for EAP, for 1) dysmenorrhea (DYS) and for 2) non menstrual pelvic pain (NMPP).

Secondary objectives include evaluation of efficacy over the last 28 days of randomized treatment up to the Month 12 visit based on the following parameters: evaluation of pain associated with sexual intercourse (dyspareunia) and defecation (dyschezia), difficulty of doing daily activities, analgesic use, assessment of subject perception of severity, change in uterine bleeding, Quality of Life (QoL) questionnaires, pharmacoeconomic burden of endometriosis by assessing changes in patient productivity, assessment of endometriosis-related number of non-study health visits, number of days in hospital and type of medical procedures performed during the Treatment Period.

Safety and tolerability objectives include assessment of bone mineral density (BMD), endometrial health, cardiac safety including QT interval prolongation, standard laboratory safety parameters, gynecological assessments and adverse event (AE) frequency including specific hypoestrogenic AEs.

Exploratory objectives include assessment of bone turnover markers and collection of pharmacokinetic (PK) and pharmacodynamic (PD) related data of linzagolix for a separate modelling exercise.

Endpoints:

Efficacy endpoints

- **Primary efficacy endpoints:**

The two co-primary, composite, efficacy endpoints are clinically meaningful reduction from baseline to the last 28 days preceding the Month 12 visit (the 4-week period preceding Month 12 visit), along with a stable or decreased use of analgesics for EAP, in the mean daily assessment of 1) DYS and of 2) NMPP, both measured on a Verbal Rating Scale (VRS) using an electronic diary (eDiary).

- **Secondary efficacy endpoints:**
- Change from baseline to Month 12 in DYS (VRS)
- Change from baseline to Month 12 in NMPP (VRS)
- Change from baseline to Month 12 in dyschezia (Numeric Rating Scale - NRS)
- Change from baseline to Month 12 in overall pelvic pain (NRS)
- Change from baseline to Month 12 in the interference of pain with the ability to perform daily activities, measured using the pain dimension of the Endometriosis Health Profile-30 (EHP-30)
- Change from baseline to Month 12 in dyspareunia (VRS)
- No analgesics use for EAP during the preceding 4-week period at each scheduled assessment
- No opiate use for EAP during the preceding 4-week period at each scheduled assessment
- Responder rate at scheduled visit other than Month 12 visit, for DYS and NMPP (VRS)
- Change from baseline to each scheduled assessment in the mean pelvic pain scores for DYS, NMPP and overall pelvic pain, during the previous 4-week period assessed on the NRS and VRS
- Change from baseline to each scheduled assessment in the number of days with moderate to severe pelvic pain during the previous 4-week period assessed on the VRS
- Change from baseline to each scheduled assessment in the mean worst pelvic pain score defined as the mean of the 5 highest daily pain scores reported during the previous 4-week period assessed on the NRS
- Change from baseline to each scheduled assessment in the mean of daily dyspareunia scores reported during the previous 4-week period on the dyspareunia VRS
- Change from baseline to each scheduled assessment in the mean of daily dyschezia scores reported during the previous 4-week period assessed on the dyschezia NRS
- Change from baseline to each scheduled assessment in non-opioid, opioid and combined analgesic use for EAP during the previous 4-week period based on pill count in the eDiary
- Change from baseline to each scheduled assessment in opioid analgesic use for EAP as reported in the eDiary during the previous 4-week period based on morphine milligram equivalent (MME)
- Change from baseline to each scheduled assessment in the number of days of analgesic use (including any class) for EAP during the previous 4-week period as assessed in the eDiary

- Change from baseline to each scheduled assessment in the number of days of opioid analgesic use for EAP during the previous 4-week period as assessed in the eDiary
- Change from baseline to each scheduled assessment in the number of pelvic pain-free days (assessed on the VRS) during the previous 4-week period
- Change from baseline to each scheduled assessment in ability to perform daily activities during the previous 4-week period, as assessed in the eDiary (daily function NRS)
- Change from baseline to each scheduled assessment in the number of days with no difficulty in doing daily activities due to EAP during the previous 4-week period as assessed in the eDiary (daily function NRS)
- Change from baseline to each scheduled assessment in the number of days when dyspareunia was a problem during the previous 4-week period (including days when sexual intercourse was avoided because of anticipation of pain) as assessed on the dyspareunia VRS
- Change from baseline to each scheduled assessment in the number of days when sexual intercourse was avoided because of anticipation of pain during the previous 4-week period as assessed on the dyspareunia VRS
- Change from baseline to each scheduled assessment in the number of days with uterine bleeding (including spotting) during the previous 4-week period measured by eDiary
- Change from baseline to each scheduled assessment in the number of days when school or work was missed due to EAP in the previous 4-week period as reported in the eDiary
- Change from baseline to each scheduled assessment in the number of days when the subject had to go to bed or lie down due to EAP in the previous 4-week period as reported in the eDiary
- Change from baseline to each scheduled assessment in the Pain, Control and powerlessness, Emotional well-being, Social support, Self-image dimensions and the Modular sexual relationship questionnaire of EHP-30 scores
- Change from baseline to each scheduled assessment in the Health-Related Productivity Questionnaire (HRPQ) scores
- Number of non-study endometriosis related health visits, number of days in hospital and type of procedures performed based on Health Resource Utilization Questionnaire (HRUQ) at each scheduled assessment
- Change from baseline to each scheduled assessment in the Physician/Subject Surgery Intention Question (PSIQ/SSIQ)
- Change from baseline to each scheduled assessment in the PROMIS Fatigue – Short Form 6a
- Change from baseline to each scheduled assessment in the EuroQoL 5-Dimension 5-Level (EQ-5D-5L) questionnaire

- Response at each scheduled assessment according to Patient Global Impression of Change (PGIC) (and Post-treatment Patient Global Impression of Change, PPGIC)
- Change from baseline to each scheduled assessment in the monthly PGIS (mPGIS) score

Safety endpoints

- Change from baseline to each scheduled assessment in BMD measured by Dual-energy X-ray Absorptiometry (DXA) of lumbar spine (L1-L4), femoral neck, and total hip
- Incidence and severity of treatment emergent adverse events (TEAEs)
- Incidence and severity of hypoestrogenic TEAEs (hot flush)
- Time to the first post-treatment menses
- Changes in clinical laboratory assessments (hematology, biochemistry, coagulation parameters, hormones, lipids and urinalysis) from baseline to each scheduled assessment
- Any pathological changes from baseline in the endometrium as assessed by histology from endometrial biopsies
- Changes from baseline to each scheduled assessment in any other safety parameter including weight, vital signs, electrocardiogram (ECG), gynecological assessments and endometrial thickness

Exploratory endpoints

- Change from baseline in bone turnover markers at each scheduled assessment
- PK and PD of linzagolix

Study Design: This is a prospective, randomized, double-blind study. Subjects who have completed the 6-month Treatment Period in the main study (18-OBE2109-003 - Edelweiss 3) will be invited to enter the present extension study. Month 6 visit of the main study is a decision point for Subjects to either end treatment and enter a post-treatment follow up (part of the main study), or to opt for a 6-month treatment extension.

The extension study starts at the Month 6 visit of the main study. Subjects will be required to sign a specific informed consent form (ICF) for this extension study. Only subjects who have completed the full 6-month Treatment Period in the main study and meet the inclusion criteria will be eligible for entry in the extension study.

All subjects will receive once daily either linzagolix 75 mg alone (with ABT placebo) or 200 mg combined with ABT for 6 months. Subjects who received placebo during the main study will be randomized to either linzagolix 75 mg alone (with ABT placebo) or linzagolix 200 mg with ABT. Subjects who received active treatment during the main study will continue with the same treatment.

Linzagolix/placebo tablets will be provided in monthly treatment kits, packaged, labelled and administered in the same manner to protect the blinded nature of the trial.

ABT/placebo treatments will be supplied as 3-monthly kits, packaged, labelled and administered in the same manner to protect the blinded nature of the trial.

After end of treatment in the extension study (6-month Treatment Period: from Month 6 to Month 12), subjects will enter a post-treatment Follow-Up Period of 6 months with no investigational medicinal product (IMP).

The total duration of the present extension study will be 12 months.

Study Population: All subjects who have completed the full 6-month Treatment Period in the main study and who meet the inclusion criteria will be invited to enter the extension study.

It is estimated that up to 288 subjects will enter the extension study, assuming that 80% of the patients randomized in the main study will complete the study (namely 360 subjects) and that up to 80 % thereof will enter the extension study.

The study will be conducted in the Unites States (US) and Europe, at the same investigational sites as in the main study.

Eligibility Criteria:

Inclusion Criteria

To be eligible for inclusion into this extension study, the subjects must **fulfil all** of the following criteria:

1. The subject must provide written informed consent specific to this study prior to starting the extension study treatment.
2. The subject has completed the 6-month treatment in the main study.
3. The subject is willing and able to continue to comply with the requirements of the study protocol for the duration of the extension study.
4. The subject agrees to continue to use only the analgesic rescue medication permitted by the protocol during the Treatment and Follow-up Periods.
5. If of childbearing potential, the subject agrees to continue to use one of the following birth control methods during the entire Treatment Period of the study and until 3 months after the end of treatment:
 - a. Sexual abstinence, if this is the subject's habitual practice and/or the subject is routinely abstinent from heterosexual intercourse,
 - b. Partner with a vasectomy with confirmed azoospermia,
 - c. Double non-hormonal barrier contraception such as condom or diaphragm each combined with spermicide.

Exclusion Criteria

To be eligible for inclusion in this extension study the subject must **not** meet any of the following criteria:

1. The subject is pregnant or is planning a pregnancy within the duration of the study (including the Follow-up Period).
2. The subject is likely to require treatment during the study with any of the medications listed below:
 - a. GnRH antagonists
 - b. GnRH agonist injections/3-month depot injections
 - c. Danazol
 - d. Oral contraceptives and other sex hormones
 - e. Depot contraceptives
 - f. Selective Progesterone Receptor Modulators (SPRMs), Selective Estrogen Receptor Modulators (SERMs) and aromatase inhibitors
 - g. Long acting narcotics (i.e. requiring less than once daily dosing)
 - h. Systemic glucocorticoid treatments for acute diseases (not depot)
 - i. In situ copper intra-uterine device (IUD)
 - j. In situ IUD with progestogen
3. The subject is likely to use cannabinoids during the study.
4. The subject has any other clinically significant gynecologic condition identified during the main study on transvaginal ultrasound (TVUS), on endometrial biopsy or at the manual breast examination, which might interfere with the study efficacy and safety objectives.
5. The subject has met any of the main study discontinuation criteria including:
 - a. Serum calcium level confirmed on a repeated fasting test above 2.9 mmol/L
 - b. BMD decrease from baseline > 8% or a Z-score \leq -2.5 at either femoral neck, hip or spine on the Month 6 DXA scan during the main study.
 - c. QTcF > 500 ms or increase > 60 ms from the highest value prior to first dose during the main study.
 - d. Any of the following elevation of hepatic enzymes:
 - ALT or AST >8xULN
 - ALT or AST >5xULN for more than 2 weeks
 - ALT or AST >3xULN and (TBL >2xULN or INR >1.5)

- ALT or AST >3xULN with the appearance of fatigue, nausea, vomiting, right upper quadrant pain or tenderness, fever, rash, and/or eosinophilia (>5%)
6. The subject has any condition that, in the opinion of the Investigator, constitutes a risk or a contraindication to the participation of the subject in this extension study, or that could interfere with the study objectives, conduct or assessments.

Investigational Medicinal Product(s) (IMP): the term “Investigational Medicinal Product” (IMP) will refer to the ObsEva investigational drug linzagolix 75 mg tablets and 200 mg tablets, the ABT (E2 1 mg/NETA 0.5 mg) capsules or their matching placebos.

Data Analysis and Statistics

The primary objective of this extension study is to assess the maintenance of efficacy of linzagolix administered orally once daily for up to an additional 6 months (for up to 12 months of treatment in total) in the subset of subjects who are treated with linzagolix up to the time point of interest. As such, the focus will be on subjects who received active treatment in the main study. The assessment of subjects who switched from placebo in the main study to active treatment in the extension study will be conducted as a secondary objective.

No formal hypothesis tests are planned for this extension study. Data will be summarized by timepoint for each treatment group. Subjects will be analyzed according to actual treatment received. The following four treatment groups will be analyzed: linzagolix 75 mg and linzagolix 200 mg with ABT fixed dose groups, linzagolix 75 mg and linzagolix 200 mg with ABT after 6 months of placebo treatment. Only subjects with assessments at both baseline and the given time points will be included in the summaries. Baseline values are the same as in the main study (18-OBE2109-003 - Edelweiss 3), i.e. data collected prior to the treatment administration in the main study.

Efficacy analysis methodology

Summaries will be performed using the Treatment Extension Analysis Set and the Follow-up Extension Analysis Set. Data from both the main study and the extension study will be summarized.

Efficacy endpoints will be derived in the same way as in the main study. The same criterion for defining a subject as being a responder by having a clinically meaningful reduction in DYS and in NMPP, along with a stable or decreased use of analgesics for EAP, will be used as per the criteria in the main study.

Safety analysis methodology

Summaries will be performed using the Extension Safety Analysis Set and the Follow-up Extension Analysis Set.

Data from both the main study and the extension study will be summarized.

Pharmacokinetic analysis methodology

Descriptive statistics of plasma concentrations will include mean (arithmetic and geometric) and standard deviation, median, 1st and 3rd quartiles, minimum, maximum, coefficient of variation (CV%) and number of observations. Concentrations below the limit of quantification (LOQ) will be assigned a value of zero. Explorative analyses of correlations between plasma concentrations and intrinsic PK

factors such as e.g. body weight/body mass index (BMI), race, age may be performed, as appropriate, and will be reported separately.

PK analyses will be based on the Extension PK Set.

Pharmacodynamic (and other) analysis methodology

Pharmacodynamic parameters, such as for example estradiol and other hormones, will be summarized by time point for each treatment group, and listed for each subject by visit day and dose regimen. Where appropriate, changes from baseline will be presented. Potential PK-PD relationships may be investigated graphically and through statistical modeling, whilst also exploring possible covariates, and will be reported separately.

Study Specific Data Analyses

End-of-Treatment Period Analysis

After all subjects have completed the Treatment Period, a complete analysis will be performed. This analysis will include all data up to the end of treatment visit. A database lock will be performed, with any discrepant data clarified before the lock.

Post-Treatment Follow-up Period Analysis

After all subjects have completed the Post-Treatment Follow-up Period, a final database lock will be performed followed by a second analysis. This analysis will include all data collected during the Post-Treatment Follow-up Period.

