Median Z scores, interquartile ranges and total ranges for femoral neck, total hip and lumbar spine at baseline, Week 24 and Week 52 did not change importantly over time: medians remained within the range of -0.20 to 0.30, 0 to 0.40, and -0.25 to 0.35 in all treatment groups for the femoral neck, total hip and lumbar spine, respectively. Median absolute change from baseline to Week 52 ranged from -0.10 to 0.00, -0.10 to 0.00 and -0.20 to -0.10, respectively.

Over the 52-week treatment period, 154/176 (87.5%) of subjects reported treatment emergent adverse events (TEAEs). The incidence of TEAEs was not dose-dependent across treatment groups, ranging from 81.8% in the 100 mg group to 93.3% in the 200/100 mg group. The majority of the TEAEs (616/846; 72.8%) were reported during the first 24 weeks of treatment.

The most commonly reported TEAEs were headache (32.4%) and hot flush (28.4%). The majority of these events occurred during the first 24 weeks of treatment. Headaches were reported with a similar frequency across treatment groups, ranging from 22.2% in the 75 mg FD group to 44.8% in the placebo/100 mg group, with no apparent dose relationship. Conversely, the incidence of hot flushes was dose-dependent and increased with increasing exposure to linzagolix: 16.7% (50 mg), 20.7% (75 mg FD), 22.2% (75 mg TD), 24.1% (placebo/100 mg), 27.3% (100 mg), and 60.0% (200/100 mg). Of note, there was no worsening in the incidence of hot flushes during the treatment extension; only 2/61 hot flush events were reported.

Ten serious AEs (SAEs) were reported in nine subjects. None of the SAEs were considered as related to study treatment. The SAEs of ruptured ectopic pregnancy (50 mg), pelvic pain (50 mg), pneumonia (75 mg TD), and anxiety disorder (200/100 mg) led to subject withdrawal from treatment during the extension phase of the study.

During treatment extension, 12 subjects (6.8%) reported 17 TEAEs leading to treatment withdrawal. In the 200/100 mg group, one subject discontinued treatment due to bone loss and one subject due to bone pain. In the 75 mg FD group, one subject discontinued treatment due to bone density decreased.

There were no subjects with AST and/or ALT values $>2 \times$ ULN during the treatment extension.

Overall, there were no clinically meaningful changes from baseline in laboratory parameters, vital signs, physical examination, or lipid measurements including HDL cholesterol, LDL cholesterol, and triglycerides in any group.

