6.6.1. Adverse Events

All AEs recorded during the course of the study will be coded according to the MedDRA dictionary (26.0) and assigned to a system organ class (SOC) and Preferred Term (PT). The NCI-CTCAE (version 4.3) will be used to grade the severity of AEs.

The following definitions will be used for the analysis of adverse events (AEs). All analysis described below will be based on the Treatment Emergent Adverse Events (TEAEs), unless otherwise specified.

	Definition
Treatment emergent adverse event (TEAE)	AEs with a start date on or after the first dose of extension study drug through 30 days after discontinuation of study drug or Month 12 visit date, or any event that was present at Month 6 but worsened in intensity or was subsequently considered drug- related by the investigator through the end of the extension study
Treatment Related TEAE/AEs	LGX-related AEs, defined as having "definite, probable or possible" relationship to study drug ABT-related AEs, defined as having "definite, probable or possible" relationship to add-back therapy
Serious Adverse Events (SAEs)	Any AE with "Serious?" = Yes in the CRF "Adverse event" page.
Adverse Events Leading to Permanent Treatment Discontinuation	Any AE action taken = Drug Withdrawn in the CRF "Adverse event" page.
Adverse Events Leading to Death	Any AE with fatal outcome

Post-Treatment Adverse Events	Adverse events starting more than 30 days
	after end of treatment

TEAEs tables will be presented for the below periods/populations:

- Extension treatment period on Extension Safety Analysis Set
- Extension follow-up period on Follow-up Safety Analysis Set,
- Combined Extension treatment and follow-up period on Follow-up Safety Analysis Set
- Combined Main treatment period and Extension treatment period on Extension Safety Analysis Set:
- Combined Main treatment period and Extension treatment period on Safety Analysis Set
- Day 1 (from main study) to end of Extension follow-up period, or end of Main follow-up period for subjects not entering extension, on Safety Analysis Set

Post-treatment AEs tables will be presented for below periods/populations:

- Combined Extension treatment and follow-up period on Follow-up Safety Analysis Set
- Extension follow-up period on Follow-up Safety Analysis Set
- Day 1 (from main study) to end of Extension follow-up period, or end of Main follow-up period for subjects not entering extension, on Safety Analysis Set

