All AEs tables will be presented for the below periods/populations:

- Day 1 (from main study) to end of Extension follow-up period, or end of Main follow-up period for subjects not entering extension, on Safety Analysis Set

Periods are defined in section 5.2

Tables based on Safety Analysis Set will use the following treatment groups, with the note that subjects can have a different time of treatment exposure (up to 6 months for subjects not in extension, up to 12 months for subjects entering extension):

- linzagolix 75 mg / linzagolix 75 mg
- linzagolix 200 mg with ABT / linzagolix 200 mg with ABT
- Placebo / linzagolix 75 mg (subject receiving placebo in main study and treated with linzagolix 75 mg in extension study)
- Placebo / linzagolix 200 mg with ABT (subject receiving placebo in main study and treated with linzagolix 200 mg with ABT in extension study)
- Placebo

If, for a subject not entering the Extension follow-up period, an AE occurs after Month 12-1 or treatment discontinuation, then the AE will be counted in the Extension treatment period.

For all study periods, an overall summary table will be prepared presenting, by treatment group, the number and percentage of subjects with

- any AE,
- any TEAE,
- any post-treatment AE (displayed only for the Extension follow-up period),
- Severe TEAE,
- any TEAE assessed by the Investigator as related to linzagolix ((definite, probable, or possible relationship),
- any TEAE assessed by the Investigator as related to add-back therapy ((definite, probable, or possible relationship),
- any TEAE leading to permanent discontinuation of IMP,
- any serious adverse event (SAE),
- any serious treatment emergent adverse event (Serious TEAE),
- any non-serious TEAE
- any serious treatment emergent adverse event (SAE) related to linzagolix,
- any serious treatment emergent adverse event (SAE) related to add-back therapy,
- any fatal TEAE (where outcome is "Fatal")

In these tabulations, each subject will contribute only once (i.e., via the most related occurrence or the most intense occurrence) to each of the incidence rates in the descriptive analysis, regardless of the number of episodes experienced.

Adverse events are summarized by subject incidence rates, therefore, in any tabulation, a subject contributes only once to the count for a given adverse event (SOC or preferred term).

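### Extension-period TEAE tables leave out unchanged, already drug-related events carried over from the main study, so hot flush columns differ in meaning between continuing and switch arms, and no table gives Month 6–12 prevalence

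*Protocol*

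**What the plan says.** Protocol 6.2 lists the frequency of hypoestrogenic AEs among the safety objectives. The synopsis and Protocol 7.2 make hot flush a named endpoint: "Incidence and severity of hypoestrogenic TEAEs (hot flush".

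SAP 6.6.1 sets the default basis for AE outputs: "All analysis described below will be based on the Treatment Emergent Adverse Events (TEAEs), unless otherwise specified". Its TEAE definition has three routes:

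- Onset: "AEs with a start date on or after the first dose of extension study drug through 30 days after discontinuation of study drug" or the Month 12 visit date.
- Worsening or later attribution: "any event that was present at Month 6 but worsened in intensity or was subsequently considered" drug-related by the investigator.

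One of the planned table sets is "Extension treatment period on Extension Safety Analysis Set". For every study period there is also an overall summary, which includes the row "any TEAE leading to permanent discontinuation of IMP". The by-subject listing of discontinuations is likewise of treatment-emergent events. Yet the definitions table in the same section describes AEs leading to permanent discontinuation as any AE whose recorded action is that the drug was withdrawn, with no condition on onset.

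SAP 6.6.1 also plans TEAE tables for the main and extension treatment periods combined, an all-AE table from Day 1 of the main study to the end of follow-up, and a listing of all AEs. SAP 6.3.1 tabulates reasons for stopping extension treatment.

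**The concern.** Take a woman on linzagolix in both studies whose hot flush began in Month 2, was rated related then, and persists at the same intensity to Month 12. She had the symptom throughout the extension but contributes nothing to the hot flush line of the extension-period TEAE tables. A woman who switched from placebo and develops the same symptom in Month 7 is counted. The four columns stand side by side, but the continuing columns show what is left to appear after six months on drug and the switch columns show first appearance on drug.

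The continuing arms are the stated focus of the analysis (Protocol 13.5), and long-term tolerability is what a 12-month extension can describe. If only onset is tabulated for Months 6–12, a low figure in those arms could mean that hot flushes resolved or that they continued unchanged. The table cannot tell these apart.

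The same filter applies to withdrawals. If a carried-over, unchanged, already related event makes a woman stop extension drug, that stop is outside the extension-period TEAE row and the TEAE listing.

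**Working it through.** **1. The plan's own figure.** Protocol 13.2: 450 × 0.80 = 360 completers, and 360 × 0.80 = 288 entering the extension. This reproduces. With equal entry from three equal main-study arms (my assumption), 288 / 3 = 96 women per continuing arm.

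**2. One event followed through the outputs.** The event is a hot flush with main-study onset, already rated related, unchanged after Month 6. It fails the onset route, the worsening route and the later-attribution route.

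| Output | Event counted? | Gives Month 6–12 hot flush prevalence? |
|---|---|---|
| Extension treatment period TEAE tables (SAP 6.6.1) | No | No: new, worsened or newly attributed only |
| Combined main + extension TEAE tables, Extension Safety Analysis Set (SAP 6.6.1) | Yes, if anchored to the first main-study dose | No: cumulative from Day 1 |
| All-AE table, Day 1 to end of follow-up (SAP 6.6.1) | Yes | No: covers the whole study |
| Listing of all AEs (SAP 6.6.1) | Yes | No: not a summary |
| Disposition reasons (SAP 6.3.1) | Only if she stops, and only as the category AE | No |

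In the combined table, a flush that resolved in Month 2 and one that lasted to Month 12 look the same.

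**3. The anchor.** The only TEAE definition in SAP 6.6.1 starts at the first extension dose. SAP 6.2.6.2 treats some main-study onsets as treatment-emergent when imputing missing dates, which implies an anchor at the first main-study dose for the combined tables. It is not stated.

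**4. Withdrawals.** Inclusion criterion 2 requires completion of main-study treatment. So within the Extension Safety Analysis Set, an AE with the drug withdrawn in the combined summary should be an extension withdrawal, whatever its onset. The gap is therefore confined to the extension-period row and the TEAE listing.

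**5. Size, as illustration.** Protocol 5.5.3 gives 19.0% with hot flush at week 24 on 75 mg in the Phase 2b study: 96 × 0.19 = 18.2 women. The share still ongoing at Month 6 is not given, so the full range is shown:

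| Share ongoing at Month 6 | Carried-over women per arm |
|---|---|
| 0% | 0 |
| 25% | 18.2 × 0.25 = 4.6 |
| 50% | 18.2 × 0.50 = 9.1 |
| 75% | 18.2 × 0.75 = 13.7 |
| 100% | 18.2 |

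If new cases after Month 6 followed the Phase 2b event ratio of 2/61, the extension-period table would show 18.2 × 2/61 = 0.6 women in that arm.

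**6. The Phase 2b figures.** Protocol 5.5.3 reports hot flush in 28.4% of 176 women (0.284 × 176 = 50) and says of the extension that "only 2/61 hot flush events were reported". That is 2/61 = 3.3% of events, or at most 2/176 = 1.1% of women.

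**The case against.** The strongest reply is that the plan already captures these events. The combined main-plus-extension tables cover the same women in the same four groups, and the all-AE table and the listing add to that. This stands: a reader might infer that carried-over hot flushes are missing from the analysis altogether, and the documents do not support that. What remains is the unstated anchor and the lack of any summary specific to Months 6–12.

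On withdrawals the reply is also largely right. The combined summary and the disposition table both show stops regardless of onset. Protocol 10.7.2.1 describes AE discontinuation in terms of a new or worsening condition, and worsening would make the event a TEAE. So a reader should not infer that AE-driven stopping is under-reported across the plan; at most one row and one listing are affected.

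Third, the endpoint is incidence, which onset counting measures, and no formal comparison of continuing with switch arms is planned. Both are true. Prevalence is therefore an addition to the endpoint, but the columns will still be printed together and read across.

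Last, a reader might take the Phase 2b 2/61 figure as proof of the artefact. It is not. The documents give neither hot flush durations nor the number ongoing at week 24. The group with the highest rate (60.0%) had its dose reduced from 200 to 100 mg on entering the extension, so real resolution is a competing explanation. The figure is consistent with the problem and no more.

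**Conclusion.** The point holds for the extension treatment-period outputs in SAP 6.6.1. Unchanged, already related events from the main study are left out of the TEAE tables, the discontinuation row and the TEAE discontinuation listing. Hot flush columns for continuing and switch arms are not comparable there, and no planned table describes hot flush burden in Months 6–12.

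The size cannot be fixed from the documents. The range of 0 to 18 women rests on equal entry across arms (96 per continuing arm), on the 75 mg Phase 2b rate applying here, and on women with hot flushes entering the extension as often as others. No rate is given for 200 mg with ABT, so the range does not cover that arm. It would go too far to say that the continuing arms will look almost free of hot flushes: that depends on the unknown ongoing share and on how many new cases arise.

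**What to change.** In SAP 6.6.1:

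1. For the extension treatment period on the Extension Safety Analysis Set, add a table of hot flush present at any time, by treatment group and worst severity. Split it into carried over (earlier onset, unresolved at the first extension dose) and new.
2. Base the extension-period discontinuation row and listing on every AE whose action taken is drug withdrawn after the first extension dose, whatever its onset date. This follows the section's own definition.
3. State that TEAEs in the combined main-plus-extension tables are anchored to the first main-study dose.

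The cost is SAP wording and one extra table. Onset and resolution dates, outcome and action taken are already collected (Protocol 12.1.1 and 12.2.3), and partial end dates already have an imputation rule (SAP 6.2.6.2). No hypothesis tests are planned, so there is no multiplicity cost. The one drawback is that carried-over status will be only as good as the recorded AE end dates.
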